The primary endpoint of the study is the difference in the Baseline-to-Week-12 % change of VH:CD ratio between each of the two AMG 714 dose arms against the placebo arm.

The primary endpoint will be tested for each of the two dose levels, 150 mg or 300 mg, separately as follows:

$H_{10}: \mu_{AMG\ 714\ (300mg)} = \mu_{Placebo}$
against the alternative

$H_{11}: \mu_{AMG\ 714\ (300mg)} \neq \mu_{Placebo}$
and

$H_{20}: \mu_{AMG\ 714\ (150mg)} = \mu_{Placebo}$
against the alternative

$H_{21}: \mu_{AMG\ 714\ (150mg)} \neq \mu_{Placebo}$

where $\mu_{AMG\ 714\ (300mg)}$, $\mu_{AMG\ 714\ (150mg)}$ and $\mu_{Placebo}$ denote the mean Baseline-to-Week-12 % change of VH:CD ratio in the high dose, low dose and placebo arm, respectively. Each of the two hypotheses will be tested using a two-sided, 0.05 level of significance without any adjustments for multiple comparisons.

6 Estimation of sample size

The sample size of approximately 63 subjects (21 subjects/arm) has been calculated to achieve at least ~ 80% power in the primary endpoint, the difference in the Baseline-to-Week-12 %-change of VH:CD ratio between the two AMG 714 arms and the placebo arm. This sample size provides close to 90% (88.8%) power to detect a 40-point difference between the placebo arm and the 300mg high-dose arm, and close to 80% (79.3%) power to detect a 35-point difference between the placebo arm and the 150mg low-dose arm.

This sample size calculation is based on the following assumptions:

- Two-sided type one error rate $\alpha = 0.05$.
- Power $1-\beta = 80\%$.
- Analysis method: one-way ANOVA by SAS® (proc power).
- Common SD = 36 for the baseline to Week 12 %-change in VH:CD.
- 45%-change (decrease) in the placebo group, %-change (decrease) of 10% in the 150mg and 5% in the 300mg arms.
- Drop-out rate ~19% (assuming non-evaluable drop-outs plus DH $\leq 15\%$ and non-evaluable due to technical issues or villous atrophy at baseline $< 5\%$).

These assumptions are based on the observations made in a similar 12-week gluten challenge study done with 3-5 grams of gluten per day (Lähdeaho *et al*, 2011). According to this sample size calculation (including a 19% drop-out rate), 17 completed evaluable subjects/arm (51 subjects in total) will be needed for the primary analysis.

7 Statistical methods

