As a secondary approach, the same model will be fitted using the absolute change in IEL density as a response variable. The modelling results (ANOVA table, parameter estimates, estimated treatment effect, marginal (i.e. least squares) means estimates and results of the check of assumptions, i.e. the check of common variance assumption) will be tabulated and 95% confidence intervals added, where appropriate.

The baseline and post-baseline values along with the change from baseline values (both relative and absolute) will also be described by summary statistics and tabulated by treatment group. Baseline and post baseline values will also be listed.

PP populations will be used for the analysis.

Attenuation of gluten-induced small intestinal mucosal morphological injury using a grouped classification of Marsh score

Marsh-Oberhuber classification (Marsh, 1992; Oberhuber, 2000) i.e. the Marsh score, a commonly used histological score with possible values 0, 1, 2, 3a, 3b, 3c with 0 being the best and 3c the worst, will be assessed at screening and Week 12 biopsies.

The Marsh scores will be analysed using a simple logistic regression model, where improvement from baseline in the Marsh score is used as dependent variable and treatment group, site and sex will be included in the model as explanatory variables. For modelling purposes, a binary variable with values 1 (in case improvement in Marsh scores was observed) and 0 (no improvement or worsening in Marsh scores) will be used as a response. Logit function will be used as the link function. The following model will be fitted:

$$\log\left(\frac{p_{jkl}}{1-p_{jkl}}\right) = \mu + \alpha_j + \varphi_k + \tau_l,$$

where

$Y_j \sim \text{Bin}(p_{jkl}, n_{jkl})$ – is the number of subjects with improvement in Marsh scores from the second biopsy in treatment group j ($j = 1, 2, 3$),

p_{jkl} is the probability of improvement in Marsh score for subjects in treatment group j sex k and site l by Week 12,

μ is the overall mean (on logit scale),

α_j is the fixed effect due to treatment j on the logit scale,

φ_k is the fixed effect due to sex k on the logit scale,

τ_l is the fixed effect due to site l on the logit scale.

The odds ratios for 150 mg AMG 714 vs placebo groups and 300 mg AMG 714 vs placebo groups will be reported and the following formula will be used for obtaining the ratios:

$$OR = \exp(\alpha_{AMG\ 714} - \alpha_{Placebo}),$$

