where $\alpha_{AMG\ 714}$ denotes the treatment effect of AMG 714 (for 150 mg AMG 714 and 300mg AMG 714 groups) on logit scale and $\alpha_{Placebo}$ denotes the placebo effect on logit scale.

The following SAS code will be used to fit the above-specified model:

```
proc genmod data=marsh descending;
  class trt site sex;
  model marsh_imp = trt site sex / dist=bin link=logit lrci type3;
  estimate 'OR 150AMG vs PLA' trt 1 0 -1 / exp;
  estimate 'OR 300AMG vs PLA' trt 0 1 -1 / exp;
  lsmeans trt / cl ilink;
  ods output ParameterEstimates=Par_est Estimates=Eff_est
    Type3=Type3
    LSMeans=Ls_mean;
run;
```

The modelling results (parameter estimates, estimated odds ratio of 150 mg AMG 714 vs placebo, estimated odds ratio of 300 mg AMG 714 vs placebo, marginal (i.e. least squares) means estimates for treatment groups) will be tabulated and 95% confidence intervals

added, where appropriate. Marginal means estimates for the probabilities will be presented on the original (probability) scale, odds ratios will also be presented.

The baseline and post-baseline frequencies of all categories of the Marsh score scale, along with change from baseline frequencies will be tabulated by treatment group. Baseline and post baseline values will also be listed.

The analysis will also include the percentage of subjects without atrophy according to the Marsh score, i.e., the % of subjects with Marsh scores 0, 1 or 2. Frequency table by treatment group will be used for summarizing these results.

PP populations will be used for the analysis.

Attenuation of gluten-induced serum antibodies: anti-tissue transglutaminase antibodies (anti-tTG) IgA

Anti-tTG auto-antibodies, while not very responsive to modest dietary transgressions, are very specific for celiac disease activity and constitute an important tool to assess disease modification (Lähdeaho *et al*, 2011; Kelly *et al*, 2013).

The relative (%) change from baseline in anti-tTG IgA result will be analysed using a linear mixed effects repeated measures model (MMRM) with the baseline value, treatment group, site, sex time point and a time point-by-treatment group interaction term as fixed effects with an underlying correlation structure between the time points that results in the best fit for the model. Subject will be included as a random effect. The following model will be fitted:

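### The Marsh dose-versus-placebo odds ratios are ML/Wald results at about 17 per arm, with no rule for an arm in which nobody, or everybody, improves

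*SAP*

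**What the plan says.** Section 7.6.2 (Marsh score) states: "The Marsh scores will be analysed using a simple logistic regression model, where improvement from baseline in the Marsh score is used" as the dependent variable. The response is "a binary variable with values 1 (in case improvement in Marsh scores was observed) and 0 (no improvement or worsening in Marsh scores". The model is ordinary binomial maximum likelihood in PROC GENMOD: "model marsh_imp = trt site sex / dist=bin link=logit lrci type3". The section undertakes to report an odds ratio for each dose against placebo, and the code obtains them from "estimate 'OR 150AMG vs PLA' trt 1 0 -1 / exp" and "estimate 'OR 300AMG vs PLA' trt 0 1 -1 / exp".

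The results named for tabulation are parameter estimates, the two odds ratios and the marginal means, with 95% intervals where appropriate. The Type 3 table is saved by the ODS statement but is not named in that list. Marsh frequencies and the percentage without atrophy are also tabulated by arm.

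On size, section 6 states that "17 completed evaluable subjects/arm (51 subjects in total) will be needed for the primary analysis". Section 3 requires all secondary endpoints to be analysed separately in PP1 and in PP2, and it describes PP2 as a small part of the study.

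No penalised, exact or other sparse-cell rule is given for this model. Several repeated-measures secondary endpoints do have a stated fallback (GEE) if parametric assumptions fail. The Marsh model has none.

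**The concern.** The logit model has six parameters: an intercept, two for treatment, two for site and one for sex. It is fitted to about 51 subjects. Section 6 expects mean VH:CD to fall in every arm, by 45% on placebo, 10% at 150 mg and 5% at 300 mg. The modelled event, improvement, therefore runs against the expected direction, most strongly on placebo. A placebo arm with no improvers is a realistic outcome.

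In that case the maximum-likelihood estimate of each dose-versus-placebo log odds ratio does not exist. The fitting algorithm stops at an arbitrary large value with a far larger standard error, and the Wald test built on that ratio has a p-value close to 1 however many drug-treated subjects improved. The statistic that the SAP says it will report would then fail in the situation most favourable to the drug. Choosing another method at that stage would be a decision made after the data were seen.

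The weakness is not tied to which change is coded as the event. Any binary Marsh response with an empty or full arm has it.

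**Working it through.** **Inputs from the SAP.** 17 evaluable per arm, 21 enrolled, drop-out about 19%, SD 36, expected changes of -45, -10 and -5 (section 6); two-sided 0.05 (section 7.2); the model and code of section 7.6.2.

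**Assumptions.** All Marsh improvement rates and the site and sex mix, because the SAP gives none.

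**Step 1: the plan's own figures.** 17/(1 - 0.19) = 20.99, so 21 per arm. The standard error of a difference is 36 x sqrt(2/17) = 12.35. The noncentrality is 40/12.35 = 3.24 and 35/12.35 = 2.83. With 48 df this gives power of 88.8% and 79.3%, exactly as stated. The 17 per arm is therefore the right basis. No power or rate is stated for the Marsh endpoint.

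**Step 2: how often the placebo arm has no improvers.** P(0 of 17) = (1 - p)^17.

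| Assumed placebo rate p | P(0 of 17) |
|---|---|
| 2% | 0.98^17 = 71% |
| 5% | 0.95^17 = 42% |
| 10% | 0.90^17 = 17% |
| 20% | 0.80^17 = 2% |

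The exponent falls with the number of subjects, so the probability is higher in PP2.

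**Step 3: what the planned model returns.** Example: 6/17 at 150 mg, 8/17 at 300 mg, 0/17 on placebo, fitted with treatment, site and sex.

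| Method, 300 mg vs placebo | Result |
|---|---|
| ML/Wald, stopped at 12 iterations | log-OR 13.16, SE 175.7, p = 0.94 |
| ML/Wald, stopped at 20 iterations | log-OR 21.16, SE 9,592, p = 0.998 |
| Firth, penalised likelihood | OR 29.1 (95% CI 3.1 to 3905), p = 0.001 |
| Fisher exact, unadjusted | p = 0.003 |

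At 12 iterations the Wald limits on the log scale are 13.16 ± 1.96 x 175.7, that is -331 to 358. For 150 mg, Firth gives OR 18.7 (1.9 to 2511), p = 0.007, and Fisher p = 0.018.

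**Step 4: what else the planned code returns on the same data.** The 2-df Type 3 likelihood-ratio test for treatment gives p = 0.0006. With placebo as the reference level, the profile-likelihood limits requested by `lrci` have lower bounds of OR 3.9 (150 mg) and 6.6 (300 mg). The upper bounds are infinite.

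**Step 5: simulated trials (17 per arm).**
- At assumed rates of 5%, 20% and 35% (placebo, 150 mg, 300 mg), power for 300 mg against placebo is 20 to 22% with the Wald contrast and 56 to 58% with Firth.
- With 5% on placebo and 35% on both doses, it is 20% for Wald, 71% for a plain 1-df likelihood-ratio test and 49% for Fisher.
- In trials with no placebo improvers, the Wald contrast was never significant.
- Under a common rate, Firth rejects in 1 to 5% of trials. The plain 1-df likelihood-ratio test rejects in about 6 to 9% at common rates of 5 to 15%, so it is somewhat liberal.

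**The case against.** A fair defence has four parts.

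1. **The planned output goes beyond Wald.** The code uses default class coding and places placebo last, so the two treatment parameters are themselves the dose-versus-placebo log odds ratios, and `lrci` gives profile-likelihood limits for each. The Type 3 test also survives an empty cell. This stands. A reader might infer that the whole Marsh analysis would collapse to p near 1, but the document does not support that: only the dose-specific Wald results behave so. The mitigation is partial, however. `lrci` does not alter the ESTIMATE lines from which the odds ratios are taken, the upper limit is infinite, and Type 3 is joint across doses and not among the listed tabulations.

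2. **Rarity of improvers is assumed.** This stands too. A reader might infer that an empty placebo arm is likely, but the SAP gives no Marsh rates. Taking section 6 at face value under normality, the chance of any VH:CD increase on placebo is P(Z > 45/36 = 1.25), or about 11%, which gives P(0 of 17) of about 15%. A Marsh category change may be rarer, but the document does not say.

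3. **Code may change without an amendment.** Section 7.6.1 allows SAS code to be modified on statistical grounds. This lowers the stakes but sets no sparse-cell rule, so the choice would still be made after seeing the data.

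4. **Firth does not give a precise estimate.** True: the intervals in the example are very wide. They do exclude 1, which the Wald interval cannot do. The tabulated frequencies would also make a 0/17 against 8/17 pattern visible.

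**Conclusion.** The point holds in a limited form. The dose-versus-placebo odds ratios that section 7.6.2 undertakes to report are ML/Wald results, and their intervals and p-values carry no information when a treatment arm has no events or all events. At 17 per arm, the chance of that on placebo runs from 2% to 71% over assumed improvement rates of 20% down to 2%, and it is higher in PP2. Where it happens, the loss is large: Wald p of 0.94 to 1.00 against about 0.001 (Firth) in the example. The joint Type 3 test and the lower profile limits remain informative, the latter provided placebo is the reference level, so the endpoint is not lost. The frequencies and power figures rest on assumed rates; the divergence itself does not. This is a minor improvement to one secondary endpoint, and the primary analysis is not affected.

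**What to change.** State in section 7.6.2 that the dose-versus-placebo odds ratios, 95% intervals and p-values come from Firth's penalised likelihood with profile-likelihood limits and penalised likelihood-ratio tests (PROC LOGISTIC with FIRTH and CLODDS=PL), in place of the Wald ESTIMATE output. At the least, make this the reported result whenever a treatment arm has no events or all events.

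The cost is a sentence of SAP text and one change of procedure. The downsides are slight shrinkage of the odds ratio toward 1 when cells are not sparse, and intervals that remain very wide when a cell is empty.

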RBC	Red blood cell
RCD-II	Type II Refractory Celiac Disease
RE	Role limitations due to emotional problems
SAE	Serious adverse event
SAP	Statistical analysis plan
SC	Subcutaneous
sCD3-	Surface CD3-negative
sCD8-	Surface CD8-negative
SD	Standard deviation
SOC	System organ class
ULOQ	Upper limit of quantification
UN	Unstructured
VT	Vitality
VH:CD	Villous height to crypt depth ratio

WBC White blood cell

WHO DD World Health Organization Drug Dictionary

1 Introduction

This is a statistical analysis plan (SAP) for study CELIM-NRCD-001 which is based on the final study protocol CELIM-NRCD-001 Version 3 (dated 29AUG2016). This SAP describes the statistical analyses which will be presented in the clinical study report.

2 Study objectives

The study objectives are the following:

The **primary objective** of the study is:

- To assess the efficacy of AMG 714 in attenuating the effects of gluten exposure in adults with celiac disease.

The **primary efficacy endpoint** is:

- Attenuation of gluten-induced small intestinal mucosal morphological injury, measured morphometrically as villous height to crypt depth (VH:CD) ratio.

The primary endpoint of the study is the difference in the Baseline-to-Week-12 % change of VH:CD ratio between each of the two AMG 714 dose arms against the placebo arm.

The **secondary efficacy endpoints** of the study are:

- Attenuation of gluten-induced small intestinal mucosal inflammation measured as intraepithelial lymphocyte (IELs) density;
- Attenuation of gluten-induced small intestinal mucosal morphological injury using a grouped classification of Marsh score;
- Attenuation of gluten-induced serum antibodies (i.e. anti-tissue transglutaminase antibodies [anti-tTG] IgA, anti-deamidated gliadin peptide antibodies [anti-DGP] IgA and IgG);
- Attenuation of gluten-induced clinical symptoms (i.e. Bristol Stool Form Scale [BSFS], Gastrointestinal Symptom Rating Scale [GSRS] and celiac disease GSRS [CeD-GSRS]).

The secondary endpoints of Marsh score and total IEL counts will be evaluated by the change from baseline to Week 12 between the two AMG 714 dose arms and the placebo arm. Anti-tTG IgA, anti-DGP IgA and IgG will be evaluated by comparing the change from baseline in results obtained after every four weeks of two AMG 714 dose arms and placebo arm. BSFS, GSRS and CeD-GSRS will be evaluated by comparing the change from baseline in weekly scores of two AMG 714 dose arms and placebo arm.

The **secondary objective** of the study is:

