The threshold of VH:CD to receive gluten challenge was initially 2 (protocol version 1) and subsequently 1.8 (protocol version 2) before the final threshold of 1.5 VH:CD was adopted in protocol version 3. The population of subjects who received gluten challenge and had pre/post biopsies, a majority of the patients, will represent the per protocol population 1 (PP1) and will be analysed for the primary and secondary endpoints separately from the subjects who did not receive gluten challenge and had pre/post biopsies, a small fraction of the subjects who will represent the per protocol population 2 (PP2). All primary and secondary endpoints will be analysed in PP1 and PP2 separately.

All subjects will complete the BSFS at the time of each bowel movement from baseline (Visit 1, Week 0/Day 0) up to the final study visit (Visit 8, Week 16/Day 112). Subjects will complete the CeD PRO daily from baseline up to the final study visit. Subjects will also complete the GSRS at screening and, thereafter, weekly from baseline through the final study visit. The BSFS, GSRS and CeD PRO will be completed using a handheld electronic diary at times specified in [Appendix 1](#).

Safety will be monitored on an ongoing basis and subjects may undergo unscheduled visits for safety reasons, if needed. Safety will be assessed throughout the study by clinical laboratory tests, physical examination, vital signs, and AE monitoring.

[Figure 1](#) represents a schematic drawing of the study periods and visits.

Figure 1 CELIM-NRCD-001 study schematic

4 Randomisation

Randomisation, i.e. the random allocation of treatments to subject numbers, will be performed according to the design of the study. A detailed description of the randomisation method, including the size(s) of randomly permuted blocks used to balance the randomisation, will be stored at the restricted area of StatFinn server, where only the randomisation expert and the unblinded statistician will have access to. Once the data base is locked and the treatment code open, the randomisation documents will be moved to the non-restricted area.

Subjects will be randomized at a 1:1:1 allocation to receive 150 mg AMG 714 or 300 mg AMG 714, or placebo once every two weeks for a total of six administrations over ten weeks. Randomization will be stratified by site and sex.

5 Statistical hypotheses

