7.1 Data sets to be analysed

The populations for analysis will be the intention to treat (ITT, safety population, at least one dose of the investigational product received) and the per protocol populations (PP, efficacy, i.e., available and evaluable pre- and post-biopsy information [Week 6]).

PP population: the PP population will exclude non-evaluable subjects and subjects with major protocol deviations thought to impact the ability to assess the effect of treatment. Exclusion of subjects from the PP set will be reviewed, documented and approved before the study is unblinded to the study Sponsor. There will be two PP populations, PP1 (including subjects who received gluten challenge for at least a week) and PP2 (including subjects who did not receive gluten challenge, or received gluten challenge for less than a week).

Non-evaluable subjects are pre-specified before database lock and will include subjects dropping out of the study before Week 6 (insufficient duration of the gluten challenge and/or no exit biopsy).

Major protocol deviations will be examined by the Sponsor prior to database lock and the decision to include or exclude subjects from PP population based on the protocol deviations will be documented.

Sensitivity analyses may be conducted, if deemed necessary, for protocol deviations such as:

1. Intake of any forbidden concomitant medication or participation in other medical procedures, in case there is reason to believe, by the judgement of the Sponsor or investigator, that such concomitant medication/procedures had a significant effect on the efficacy data obtained. For example, analgesics/anti-diarrheals which may affect symptoms;
2. Significant deviations from the inclusion/exclusion criteria or study conduct., including, but not limited to, subjects who missed one or more doses of study drug, were not fully compliant with the gluten challenge, or had dermatitis herpetiformis.

ITT population: this population consists of all randomized subjects who have received at least one dose of the study drug. Subjects will be analyzed in the treatment group to which they are randomized. Safety population is by definition the same as the ITT population. If a subject had a misallocated treatment on a specific visit observed upon unblinding, a secondary sensitivity analyses will be performed on an as treated basis.

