7.6.2 Secondary efficacy variables

The secondary efficacy endpoints of the study are:

- Attenuation of gluten-induced small intestinal mucosal inflammation measured as intraepithelial lymphocyte (IELs) density;
- Attenuation of gluten-induced small intestinal mucosal morphological injury using a grouped classification of Marsh score;
- Attenuation of gluten-induced serum antibodies (i.e. anti-tissue transglutaminase antibodies [anti-tTG] IgA, anti-deamidated gliadin peptide antibodies [anti-DGP] IgA and IgG);
- Attenuation of gluten-induced clinical symptoms (i.e. Bristol Stool Form Scale [BSFS], Gastrointestinal Symptom Rating Scale [GSRS] and celiac disease GSRS [CeD-GSRS]).

Attenuation of gluten-induced small intestinal mucosal inflammation measured as intraepithelial lymphocyte (IELs) density

Relative (%) change in IELs density will be analysed using the same method as for the primary endpoint, i.e. the following model will be fitted:

$$Y_{ijkl} = \mu + \beta \cdot \text{baseline IEL}_{ijkl} + \alpha_j + \varphi_k + \tau_l + \varepsilon_{ijkl},$$

where

Y_{ijkl} is the relative (%) change from baseline in IEL density for subject i ($i = 1, \dots, n_{ijkl}$) from site l ($l = 1, 2, 3$), sex k ($k = 1, 2$) and treatment group j ($j = 1, 2, 3$),

μ is the overall mean,

β is the parameter estimate of baseline IEL,

α_j is the fixed effect due to treatment j ,

φ_k is the fixed effect due to sex k ,

τ_l is the fixed effect due to site l ,

ε_{ijkl} is the random error for subject i from site l ($l = 1, 2, 3$), sex k ($k = 1, 2$) and treatment group j ; $\varepsilon_{ijkl} \sim N(0, \sigma_\varepsilon^2)$.

The following SAS code will be used to fit the above-specified model:

```
proc glm data=IEL alpha=0.05 outstat=F_tests;
  class trt site sex;
  model IEL_change = blIEL trt site sex / clparm solution SS1 SS2;
  estimate "150 mg AMG 714 vs Placebo" trt 1 0 -1;
  estimate "300 mg AMG 714 vs Placebo" trt 0 1 -1;
  lsmeans trt /cl stderr;
  ods output ParameterEstimates=Par_est LSMeanCL=LS_meanCL
        LSMeans=LS_mean OverallANOVA=ANOVA Estimates=Eff_est;
run;
```

The modelling results (ANOVA table, parameter estimates, estimated treatment effect, marginal (i.e. least squares) means estimates and results of the check of assumptions) will be tabulated and 95% confidence intervals added, where appropriate.

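### In PP1 the only modelled Marsh response is improvement, so an unchanged subject counts like a worsened one and the odds ratio is an insensitive measure of attenuated gluten injury

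*SAP*

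**What the plan says.** - **Endpoint.** SAP section 7.6.2 names it as "Attenuation of gluten-induced small intestinal mucosal morphological injury using a grouped classification of Marsh score". Section 2 adds how it is judged: "The secondary endpoints of Marsh score and total IEL counts will be evaluated by the change from baseline to Week 12".
- **Response.** The Marsh part of section 7.6.2 fits one logistic regression, on "a binary variable with values 1 (in case improvement in Marsh scores was observed) and 0 (no improvement or worsening in Marsh scores". The scale runs from 0 (best) through 1, 2, 3a and 3b to 3c (worst).
- **Model.** The code is "model marsh_imp = trt site sex / dist=bin link=logit lrci type3". The terms are treatment, site and sex; baseline Marsh is not among them. Odds ratios against placebo come from two ESTIMATE statements, one per dose.
- **Other Marsh output.** Category counts are tabulated, "along with change from baseline frequencies will be tabulated by treatment group", and the share of subjects at Marsh 0, 1 or 2 (no atrophy) goes into a frequency table. Neither carries a treatment contrast or an interval.
- **Populations.** Section 3 states: "All primary and secondary endpoints will be analysed in PP1 and PP2 separately". PP1 had the gluten challenge for at least a week. Section 7.1 defines the other set as "PP2 (including subjects who did not receive gluten challenge, or received gluten challenge for less than a week".
- **Expected course.** Section 6 assumes "45%-change (decrease) in the placebo group, %-change (decrease) of 10% in the 150mg and 5% in the 300mg arms", the figures being mean changes in VH:CD.

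**The concern.** PP1 subjects are deliberately exposed to gluten, and the plan expects the average mucosa to deteriorate in all three arms. A drug that attenuates this injury shows its effect mostly as subjects who stay where they were while placebo subjects get worse. The Marsh model gives both outcomes the value 0, so it credits the drug only when a score gets better. A subject who starts at Marsh 0 cannot get better at all, and without a baseline term the model cannot separate such subjects from those with room to improve.

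At stake is the only inferential Marsh result in the larger efficacy population. A drug that protects the mucosa without improving it could show little on this odds ratio, and the tables that would reveal the protection come with no estimate or interval to set beside it.

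**Working it through.** **1. The plan's own figures.** Section 6 gives SD 36, 17 evaluable subjects per arm, two-sided 0.05 and a one-way ANOVA. The standard error of a pairwise difference is 36 × √(2/17) = 12.35.
- 40 points: noncentrality 40/12.35 = 3.24; with 48 error degrees of freedom, power is 88.8% (stated 88.8%).
- 35 points: noncentrality 35/12.35 = 2.83; power is 79.3% (stated 79.3%).

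The inputs reproduce, so they can be reused. The SAP states no rate or power for the Marsh endpoint.

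**2. What the coding does, without any assumed mapping.** Suppose improvement is equally common in both arms and the drug only prevents worsening. The true improvement odds ratio is then exactly 1, whatever the protection. Example with assumed rates (improved/unchanged/worsened): placebo 5/35/60%, active 5/80/15%. Exact Fisher power at 17 vs 17 is about 0% on improvement and 70% on worsening.

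**3. Illustration from the planning means.** Assumption: a Marsh grade moves up or down when the VH:CD % change passes −c or +c, with change distributed N(−45, 36) on placebo, N(−10, 36) on 150 mg and N(−5, 36) on 300 mg. For mean m:
- P(improved) = 1 − Φ((c − m)/36)
- P(worsened) = Φ((−c − m)/36)

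At c = 20:
- Placebo improved: 1 − Φ(65/36) = 3.5%. Placebo worsened: Φ(25/36) = 75.6%.
- 300 mg improved: 1 − Φ(25/36) = 24.4%. 300 mg worsened: Φ(−15/36) = 33.8%. Unchanged: 100 − 24.4 − 33.8 = 41.8%.
- Of the 300 mg subjects coded 0, the unchanged share is 41.8/(41.8 + 33.8) = 55%.

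**4. Power.** All 17 vs 17 tables were enumerated for 300 mg vs placebo, two-sided 0.05, with no covariates and no ceiling at Marsh 0 or 3c. Wald is the test that the planned ESTIMATE statements give; a table with an empty cell counts as not significant. Fisher is shown as a check that does not break down with empty cells.

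| c | Improved, placebo / 300 mg | Worsened, placebo / 300 mg | Wald: improvement vs worsening | Fisher: improvement vs worsening |
|---|---|---|---|---|
| 0 | 10.6 / 44.5% | 89.4 / 55.5% | 42 vs 42% | 48 vs 48% |
| 20 | 3.5 / 24.4% | 75.6 / 33.8% | 4 vs 72% | 25 vs 60% |
| 40 | 0.9 / 10.6% | 55.5 / 16.5% | 0 vs 63% | 2 vs 55% |

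At c = 0 nobody is unchanged and the two codings coincide. The gap opens as more subjects stay in their grade. Part of the Wald gap is sparsity: at c = 20 the chance of no placebo improver among 17 is (1 − 0.035)^17, about 54%, and the odds ratio then has no finite estimate. Fisher shows a smaller gap in the same direction.

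**5. Direction.** In every row improvement is more frequent on 300 mg than on placebo, so the improvement odds ratio favours the drug.

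**The case against.** The strongest reply is that little depends on this. It is one secondary endpoint in a Phase 2a trial. Mucosal injury is already tested by the VH:CD ANCOVA on relative and absolute change, and inflammation by the IEL models. Marsh worsening is tabulated by arm; only a modelled contrast is missing. That limits the weight of the point but does not remove it, because the one Marsh estimate with an interval still ignores the outcome that the endpoint names.

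The illustration can also be attacked. The SAP does not link Marsh grades to VH:CD cut-offs, and it treats 0, 1 and 2 alike as being without atrophy, so steps within that range need not follow villous change. This is right: the percentages show a mechanism and are not forecasts. Ceilings cut both ways too. On the Fisher scale at c = 20, if half the subjects start at Marsh 0, power on improvement falls from 25% to 4%; if 10% start at 3c, power on worsening falls from 60% to 49%. Both shares are assumed.

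Section 7.9 lists baseline histology among possible subgroup analyses. These are optional and define no other Marsh response. PP1 may also include some subjects with low baseline VH:CD whose challenge was interrupted after a week or more. Improvement is a sensible response for them, which is a reason to keep it as a supportive analysis.

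A reader might infer that the improvement odds ratio points the wrong way or carries no information. The documents do not support that: under the section 6 means it favours both doses. Nor is improvement a poor response everywhere. In PP2, with little or no challenge, it is coherent.

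**Conclusion.** The point holds as a loss of sensitivity in PP1. The coding, the missing baseline term and the absence of any contrast on worsening follow directly from section 7.6.2. That staying unchanged is the main form of benefit follows from the challenge design and the means in section 6. The size is uncertain because no Marsh rates are given: in the illustration it runs from no loss (cut-off 0) to Fisher power of 2% against 55% (cut-off 40). It depends on the assumed mapping, on 17 evaluable subjects per arm, and on leaving out covariates and ceilings.

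This should be fixed but is not critical. It does not bias the result, reverse its direction or touch the primary VH:CD analysis. A reader might also infer that the planned logistic method has to be replaced throughout. The coding problem does not require that; sparse cells are a separate matter.

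**What to change.** Before unblinding, add to section 7.6.2 for PP1:

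- **Response.** 1 = any increase in Marsh grade from baseline to the second biopsy, on the order 0 < 1 < 2 < 3a < 3b < 3c; 0 = unchanged or improved.
- **Model.** Logistic regression with treatment, site, sex and baseline Marsh as one binary term (0-2 vs 3a-3c, the split the SAP already uses for absence of atrophy).
- **Reporting.** Odds ratios of each dose against placebo with 95% intervals, named as the main PP1 Marsh result.
- **Improvement model.** Keep it as planned for PP2 and as supportive in PP1.

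Firth-penalised estimation is optional, as a separate safeguard against sparse cells. If it is wanted, name it in advance.

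The cost is a short SAP change and one derived variable, with no new data. The downsides are one more covariate in a small model, and that a subject at 3c at baseline cannot worsen.
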